1.2.1 Clinical Experience

B244 is being developed as a 'live topical' to provide a natural source of AOB and NO/NO₂ to the human skin. A phase 1b/2a clinical trial entitled A Double Blind, Vehicle-Controlled, Single Center, Randomized, Sequential, Ascending 14-Day Multiple Dose Study in Subjects with Acne Vulgaris to Evaluate the Safety, Tolerability and Preliminary Efficacy of B244 Delivered as a Topical Spray was completed in 2016 where 36 participants with clinical diagnosis of facial acne vulgaris were randomized to receive ascending doses of investigational product (IP) over 14 days. Safety analyses have been completed and there have been no attributable drug related SAEs reported. In addition, a Phase 2b/3 clinical trial entitled A Randomized, Double Blinded, Phase IIb/III, Decentralized Study of B244 Delivered as a Topical Spray to Determine Safety and Efficacy in Participants with Mild to Moderate Acne Vulgaris in 372 patients with clinical diagnosis of facial acne has been completed. B244 was safe and well tolerated with no attributable drug related SAEs. Efficacy was supported by statistically significant 2-point reduction in IGA with B244 and a trend in the reduction of the number of inflammatory lesions compared to vehicle.

Additionally, other topical development programs with B244 include hypertension and atopic dermatitis. A study titled, “A Prospective, Controlled, Double Blinded, Multicenter, Randomized, Vehicle controlled, Phase II Study of B244 delivered as a topical spray to Determine Safety and Efficacy in Subjects with elevated blood pressure” has been completed. Safety data indicated that B244 was safe and well tolerated. Overall, 16% subjects experienced at least 1 TEAE during the study with comparable incidence in the B244 and Vehicle groups. The most commonly reported types of events in the study were nervous system disorders (5% incidence) and investigations (4% incidence). No TEAE was reported in more than 1 subject in the B244 group. There was no apparent increase in the incidence of TEAEs with increasing dose in either treatment group. All TEAEs were Grade 1 or Grade 2 in severity. There were no deaths in the study. Overall, there were no unexpected safety signals observed following treatment with B244.

A study titled, “A Prospective, Vehicle Controlled, Double Blind, Multicenter, Randomized, Phase II Study of B244 Delivered as a Topical Spray to Determine Safety and Efficacy in Subjects with Mild to Moderate Atopic Dermatitis” is currently enrolling subjects.

Furthermore, a nasal spray of B244 is being developed for treatment of allergic rhinitis and migraines. A rat toxicology study performed by intranasal administration of B244 twice daily for 28 days found that B244 was safe and well tolerated in rats at levels of up to the maximum dose 8×10^9 cell/mL. A study titled, “A Prospective, Controlled, Double Blinded, Single Center, Randomized, 3 arm, Phase 1b/2a Study to Assess the Safety, Tolerability, and Preliminary Efficacy of B244 Delivered as an Intranasal Spray in Healthy Volunteers and Subjects with Seasonal Allergic Rhinitis” has been initiated. In addition, a study titled “A Prospective, Randomized, Vehicle-Controlled, Double-Blind, Phase 2 Study to Assess the Safety, Tolerability, and Efficacy of B244 Delivered as an Intranasal Spray for Preventive Treatment in Subjects with Episodic Migraine” is being initiated.

1.2.2 Safety Profile

To date, there have been no reported infections or health risks associated with topical application or ingestion of *Nitrosomonas* species. The absence of any illnesses attributed to these bacteria despite our widespread exposure indicates that they pose a minimal health risk, if any at all. Infection or tissue damage by *Nitrosomonas* is unlikely, because the sequenced genomes of several *Nitrosomonas* and other AOB lack genes encoding cytotoxins, or other known bacterial virulence factors. Further, AOB are slow growing, as compared to most heterotrophic bacteria, with optimum doubling times of 8 hours or higher. In particular, *Nitrosomonas* growth is rate limited by the availability of ammonia requiring the oxidation of 27 moles NH_3 /mole CO_2 fixed. Due to their dependence on ammonia for their growth, the numbers of *Nitrosomonas* on the skin will be necessarily limited and naturally regulated by the amount of ammonia produced in sweat. This would ensure that the amount of nitrite and NO generated would be relatively low, without any adverse effects.

2 STUDY OBJECTIVES

2.1 Study Objectives

2.1.1 Primary Objective

- To assess the safety and tolerability of B244 applied twice daily (BID) to the face for 8 weeks in subjects with mild to moderate rosacea.

2.1.2 Exploratory Objectives

- To assess the efficacy of B244 in subjects with mild to moderate rosacea.
 - Proportion of subjects with IGA improvement at Week 8 relative to baseline.
 - Proportion of subjects with CEA improvement at Week 8 relative to baseline.
 - Change in IGA from Week 8 to Baseline.
 - Change in CEA from Week 8 to Baseline.
 - Proportion of Subjects with improvement in IGA or CEA at Week 1, Week 4, and Week 12.
 - Change in Skindex 16 patient reported outcome from Baseline to Week 1, Week 4, Week 8, and Week 12.
 - Proportion of subjects with change in PSA at Week 1, Week 4, Week 8 and Week 12 from Baseline.
 - Evaluation of Telangiectasia Score at Baseline/Day 1 and Week 8

3 STUDY ENDPOINTS

3.1 Safety & tolerability

- Safety and tolerability endpoints will consist of all adverse events reported during the study duration.

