4 INVESTIGATIONAL PLAN

4.1 Study Design

- This is a Prospective, Vehicle Controlled, Double Blind, Multicenter, Randomized Phase II trial, Comparing the effect of twice daily B244 application for 8 weeks vs. vehicle application on treatment of mild to moderate rosacea.
- We will enroll approximately 130 subjects and complete 104 subjects.
- At Screening and Baseline:
 - All subjects must have clinical diagnosis of mild to moderate rosacea.
 - Subjects must have IGA score of 2-3 and CEA score of 2-3 in order to qualify for the study.
- After screening and recruitment, participants will be randomized to active or vehicle application for 8 weeks.
- Subjects will apply a total of 4 pumps of IP per application to the face twice-a-day.
- Randomization will be 1:1 B244 to Vehicle.
- Subjects will be provided with cleanser and moisturizer to use for the duration of the study.
- All B244 randomized subjects will be treated at the dose of 4×10^9 cells/ml via spray application.
- Screening will occur at Days -21 to -1.
- Washout will occur after Screening visit (Days -14 to -1).
- Randomization will occur during the baseline visit for the study (Day 1).
- Efficacy will be assessed using Investigator Global Assessment (IGA) score, Clinician’s Erythema Assessment (CEA) score, Patient Self-Assessment (PSA) score and patient reported Skindex 16.
- Clinical assessments of response to treatment will be made at Week 1 (Day 7), Week 4 (Day 28), and Week 8 (Day 56).
- At Baseline visit, subjects will receive a kit containing the drug product. Each bottle will be used for 2 weeks. At Week 4, subjects will return the used bottles from the kit and will be issued a new kit of drug product to be used from Week 4 through Week 8.
- Subjects will stop applying investigational product at Week 8 and will return investigational product at that visit.

- Subjects will come back for a 4-week post-treatment follow up visit at Week 12 (Day 84).
- Participant's safety will be monitored throughout the study. Safety will be assessed by monitoring reported adverse events, vital signs, clinical chemistry and hematology and overall tolerability of the investigational product.
- Subjects would be required to discontinue the investigational product under the following circumstances:
 - Development of an intercurrent illness that would jeopardize the safety, or significantly affect assessments of clinical status of a subject

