6.7.6 Safety Parameters

Safety and tolerability endpoints will consist of all adverse events (AEs) reported during the study duration from the date of randomization through Week 12 (End of Study Visit).

Specific AEs are defined below.

Treatment-Emergent Adverse Events (TEAE): Any AE with onset after the first dose of study medication through 56 days after the last dose of study medication.

Serious Adverse Event (SAE): An AE occurring at any dose that results in any of the following outcomes: death, a life-threatening AE, in-patient hospitalization or prolongation of existing hospitalization, a persistent or significant disability/incapacity, or a congenital anomaly/birth defect.

Associated with Use of the Study Drug: There is a reasonable possibility that the experience may have been caused by the study drug. If the Investigator does not know whether or not study drug caused the event, then the event will be handled as “related to study drug” for reporting purposes. The determination of whether an AE is related to study drug is as follows:

- Related: The AE has a missing, unknown, possible, probable or definite relationship to the study medication.
- Not related: The AE is unlikely or definitely unrelated to the study drug.

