10.1.3 Safety

Display Number	Title	Population	Unique/Repeat
14.3.1	Overall Summary of Treatment Emergent Adverse Events	Safety	Unique
14.3.1.1	Summary of Treatment Emergent Adverse Events by System Organ Class and Preferred Term	Safety	Unique
14.3.1.2	Summary of Treatment Emergent Adverse Events by System Organ Class, Preferred Term and Severity	Safety	Repeat
14.3.1.3	Summary of Treatment Emergent Adverse Events by System Organ Class, Preferred Term and Relationship to Study Drug	Safety	Repeat
14.3.2	Summary of Serious Adverse Events by System Organ Class and Preferred Term	Safety	Repeat
14.3.3	Summary of Deaths	Safety	Unique

Table 14.3.1
 Overall Summary of Treatment Emergent Adverse Events.
 Safety Population

	Statistics	B244 Topical Spray n (%)	Placebo n (%)	All Patients n (%)
Total Number of TEAEs	N	xx	xx	xx
Total Number of TESAEs	N	xx	xx	xx
Number of Subjects with:				
At Least One TEAE	n (%)	xx (xx.x)	xx (xx.x)	xx (xx.x)
At Least One Related TEAE	n (%)	xx (xx.x)	xx (xx.x)	xx (xx.x)
At Least One Severe (Grade 3) TEAE	n (%)	xx (xx.x)	xx (xx.x)	xx (xx.x)
At Least One TEAE Leading to Discontinuation	n (%)	xx (xx.x)	xx (xx.x)	xx (xx.x)
At Least One TEAE Leading to Death	n (%)	xx (xx.x)	xx (xx.x)	xx (xx.x)
At Least One TESAE	n (%)	xx (xx.x)	xx (xx.x)	xx (xx.x)
At Least One Related TESAE	n (%)	xx (xx.x)	xx (xx.x)	xx (xx.x)

Protocol: RB244-001
 Confidential

STATISTICAL ANALYSIS PLAN

 Version 2
 02-Apr-19

NOTE: The percentages are based on the number of Safety Population.

Snapshot Data DD-MMM-YYYY

CRF pages

Source: <Dataset>

Program Name: <Pgm name>

Table 14.3.1.1
 Overall Summary of Treatment Emergent Adverse Events by System Organ Class and Preferred Term
 Safety Population

	Statistics	B244 Topical Spray n (%)	Placebo n (%)	All Patients n (%)
Total Number of TEAEs	n	xx	xx	xx
Number of Subjects with at Least One TEAE	n (%)	xx (xx.x)	xx (xx.x)	xx (xx.x)
System Organ Class #1	n (%)	xx (xx.x)	xx (xx.x)	xx (xx.x)
Preferred Term #1	n (%)	xx (xx.x)	xx (xx.x)	xx (xx.x)
Preferred Term #2	n (%)	xx (xx.x)	xx (xx.x)	xx (xx.x)
Preferred Term #3	n (%)	xx (xx.x)	xx (xx.x)	xx (xx.x)
etc.				
System Organ Class #2	n (%)	xx (xx.x)	xx (xx.x)	xx (xx.x)
Preferred Term #1	n (%)	xx (xx.x)	xx (xx.x)	xx (xx.x)
Preferred Term #2	n (%)	xx (xx.x)	xx (xx.x)	xx (xx.x)
Preferred Term #3	n (%)	xx (xx.x)	xx (xx.x)	xx (xx.x)
etc.				

NOTE: The percentages are based on the number of Safety Population.

Snapshot Data DD-MMM-YYYY

CRF pages

Source: <Dataset>

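### The primary safety tables pool on-product and post-product adverse events as crude percentages; a split by onset and exposure-adjusted rates should be added beside them

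*Protocol*

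**What the plan says.** - **Objective.** Protocol 2.1.1: "To assess the safety and tolerability of B244 applied twice daily (BID) to the face for 8 weeks".
- **Endpoint.** Protocol 3.1: "Safety and tolerability endpoints will consist of all adverse events reported during the study duration". SAP v2 3.2.1 repeats this under a heading that marks it primary.
- **Exposure.** Protocol 4.1: "Subjects will stop applying investigational product at Week 8". The last visit is at Week 12 (Day 84), four weeks later.
- **TEAE window.** SAP v2 6.7.6: "Any AE with onset after the first dose of study medication through 56 days after the last dose of study medication". The same section ends the safety endpoint at Week 12. Protocol 12.4 ends AE collection at Week 12. Protocol 11.2.1 has AEs followed to 30 days after study conclusion or until judged stable, whichever is later.
- **Tables.** SAP v2 Tables 14.3.1 to 14.3.2 give event counts and subject percentages by arm, with the footnote "NOTE: The percentages are based on the number of Safety Population". None separates events by onset during or after application, and no person-time rate or time-to-first-event analysis is planned. SAP v2 8.2.1 makes the reporting descriptive and starts the summaries at first dose.
- **Follow-up.** Protocol 4.2 assumes 20% dropout overall and gives no figure by arm. Under Protocol 10.2.9, subjects who leave before Week 12 are asked to complete an Early Termination Visit.

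**The concern.** The stated question is what happens during 8 weeks of application. No planned table answers it directly, because each percentage covers the treatment period and the follow-up together. A reader of the report will probably take that single percentage as the AE incidence under 8 weeks of B244.

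Two distortions are possible. First, events after the last application may be mostly background and fall on both arms alike, so an excess confined to the application period would look smaller relative to vehicle. Second, someone who leaves early counts as a full denominator but has less time to report an event, so a difference in dropout between arms can move the percentages with no true difference in risk. Safety is the trial's only primary objective, and a split by onset made after unblinding would be post hoc.

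**Working it through.** **The plan's own figure.** 104 completers at 20% dropout: 104 / (1 − 0.20) = 130 enrolled, as stated; at 1:1 this is 65 per arm. The plan states no AE rate, precision or power for safety.

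**Share of time off product, for a completer.** To Week 12: (84 − 56) / 84 = 33%. If the 56-day rule could be applied in full: 56 / (56 + 56) = 50%. That rule would run to Day 56 + 56 = 112, beyond the Day 84 end of collection.

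**Attenuation.** These inputs are assumptions: a constant background hazard giving 12-week vehicle risk R, doubled by B244 during the 8 weeks on product and equal to vehicle afterwards, with no dropout. R = 16% borrows the only AE incidence in the documents (the completed blood-pressure study, Protocol 1.2.1, whose duration is not given). R = 30% is a second assumed value.

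- On product: vehicle 1 − (1 − R)^(8/12); B244 1 − (1 − R)^(16/12)
- Pooled to Week 12: vehicle R; B244 1 − (1 − R)^(20/12), where 20 = 8 × 2 + 4

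| R | Window | Vehicle | B244 | Ratio | Difference (points) |
|---|---|---|---|---|---|
| 16% | 8 weeks on product | 10.97% | 20.74% | 1.89 | 9.8 |
| 16% | pooled 12 weeks | 16.00% | 25.22% | 1.58 | 9.2 |
| 30% | 8 weeks on product | 21.16% | 37.85% | 1.79 | 16.7 |
| 30% | pooled 12 weeks | 30.00% | 44.81% | 1.49 | 14.8 |

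The pooled event-rate ratio falls from 2 to 20/12 = 1.67.

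Sensitivity: with the vehicle risk set over 8 weeks instead, at 5% the ratio falls from 1.95 to 1.63 and the difference from 4.7 to 4.6 points. At 50% they fall from 1.50 to 1.27 and from 25.0 to 17.7 points. The ratio is attenuated throughout; the difference moves much only when AEs are common.

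**Unequal follow-up, no true difference.** Assume dropout unrelated to AEs and spread evenly over 12 weeks. A completer has risk R. A dropout has average risk M = 1 − R / (−ln(1 − R)). The crude percentage is (1 − d)R + dM, so dropout of d1 against d2 shifts the comparison by (d1 − d2)(R − M).

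- R = 16%: M = 1 − 0.16/0.1744 = 8.2%. 25% vs 15% shifts 0.8 points; 30% vs 10% shifts 1.6.
- R = 50%: M = 1 − 0.50/0.6931 = 27.9%. The shifts are 2.2 and 4.4 points.
- 20% vs 20%: zero.

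**Limits of the dropout effect (simulation, 16% vehicle risk over 8 weeks).** With 30% dropout on B244 and 10% on vehicle, a true on-product hazard ratio of 1.15 is masked (21.6% vs 21.9%). A ratio of 1.5 (25.6% vs 22.0%) or 2 (31.1% vs 21.9%) still shows B244 as worse. If 40% of B244 subjects with an AE leave because of it, the any-AE percentage is 35.3%, against 35.4% with no dropout, because the first event is already counted.

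**After the fix.** With equal hazards, R = 30% and dropout of 30% vs 10%, simulated crude percentages are 25.7% vs 28.6%, while the exposure-adjusted rates are both 2.97 per 100 subject-weeks.

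**The case against.** The best defence is that counting every AE through follow-up is an inclusive and legitimate way to judge an 8-week course, and that the report will give other clues. SAP v2 7.4 summarises days of administration by arm. Table 14.1.1.2 shows completion of each visit and discontinuation reasons by arm. Table 14.3.1 has rows for related TEAEs and for TEAEs leading to discontinuation, and Table 14.3.1.3 splits by relationship. Under SAP v2 6.1, listings carry days relative to treatment start. The plan computes no risk ratio and makes no AE test. On the percentage scale it does report, the loss is 0.55 points at 16% background (about 0.4 of one subject among 65) and 1.87 points at 30% (about 1.2 subjects).

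Most of this stands. It limits the size of the problem and rules out demoting the whole-study summary. B244 is described as a live topical, the documents do not say how long it persists, and a lead summary cut exactly at last application would move events arising just after stopping out of the headline. What does not stand is the idea that these displays replace the missing one: none gives AE incidence by onset during and after application, and none puts events over time at risk.

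A reader might also infer that the arm with more dropout will look safer. The documents do not support that. They give only an overall 20%, equal dropout produces no bias, and AE-driven departures leave the any-AE percentage essentially unchanged.

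**Conclusion.** The point holds as a gap in presentation that is cheap to close. The primary objective is tied to 8 weeks of application, the tables pool that period with follow-up, and no planned display separates them or adjusts for time at risk.

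The size is conditional. Attenuation requires a B244 excess that stops with the product, which the documents do not establish; the split would show whether it does. Under the assumed doubling it is clear on the ratio scale (1.89 to 1.58, or 1.79 to 1.49) and modest on the percentage-point scale at these risks. The dropout effect requires non-AE dropout that differs by arm, and is then about 0.8 to 4.4 points over the ranges tried.

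A reader might infer that the primary safety result is invalid, or that every subject contributes at least four weeks off product. Neither follows. Reporting is descriptive, so no test, alpha or sample size is affected, and the four weeks apply to completers; an early withdrawal may have almost none.

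The AE windows are a firmer defect. SAP v2 6.7.6 gives both Week 12 and 56 days after last dose, Protocol 12.4 gives Week 12, and Protocol 11.2.1 gives 30 days after study conclusion or later. Protocol 11.2.1 may be meant only for following events already open, but the text does not say so.

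**What to change.** In SAP v2 8.2.1 and Tables 14.3.1 to 14.3.2:

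1. Keep the whole-study summary.
2. Add two pre-specified blocks by onset: first to last application, and after last application.
3. Add for each arm an exposure-adjusted rate in each block: subjects with at least one event per 100 subject-weeks, with time counted to the first event or the end of that window.
4. Reconcile Protocol 11.2.1, Protocol 12.4 and SAP v2 6.7.6, so that one window defines a TEAE and the second block has a defined end.

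The data are already collected: AE onset dates under Protocol section 12, and application dates in the diary under Protocol 11.2.6.1. The cost is SAP wording, repeats of existing table programs, and extra blocks to read.

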3.2 Efficacy

- IGA score at Baseline to Week 1, Week 4, Week 8 and Week 12.
- CEA score at Baseline to Week 1, Week 4, Week 8 and Week 12.
- Skindex 16 patient reported outcome from Baseline to Week 1, Week 4, Week 8 and Week 12.
- PSA score at Baseline to Week 1, Week 4, Week 8 and Week 12.

3.3 Exploratory

- IGA treatment success, defined as “clear” or “almost clear” with a 2-grade improvement in IGA score from baseline to the end of treatment.
- CEA treatment success defined as “clear” or “almost clear” with a 2-grade improvement in CEA score from baseline to the end of treatment.

4 INVESTIGATIONAL PLAN

4.1 Study Design

- This is a Prospective, Vehicle Controlled, Double Blind, Multicenter, Randomized Phase II trial, Comparing the effect of twice daily B244 application for 8 weeks vs. vehicle application on treatment of mild to moderate rosacea.
- We will enroll approximately 130 subjects and complete 104 subjects.
- At Screening and Baseline:
 - All subjects must have clinical diagnosis of mild to moderate rosacea.
 - Subjects must have IGA score of 2-3 and CEA score of 2-3 in order to qualify for the study.
- After screening and recruitment, participants will be randomized to active or vehicle application for 8 weeks.
- Subjects will apply a total of 4 pumps of IP per application to the face twice-a-day.
- Randomization will be 1:1 B244 to Vehicle.
- Subjects will be provided with cleanser and moisturizer to use for the duration of the study.
- All B244 randomized subjects will be treated at the dose of 4×10^9 cells/ml via spray application.
- Screening will occur at Days -21 to -1.
- Washout will occur after Screening visit (Days -14 to -1).
- Randomization will occur during the baseline visit for the study (Day 1).
- Efficacy will be assessed using Investigator Global Assessment (IGA) score, Clinician’s Erythema Assessment (CEA) score, Patient Self-Assessment (PSA) score and patient reported Skindex 16.
- Clinical assessments of response to treatment will be made at Week 1 (Day 7), Week 4 (Day 28), and Week 8 (Day 56).
- At Baseline visit, subjects will receive a kit containing the drug product. Each bottle will be used for 2 weeks. At Week 4, subjects will return the used bottles from the kit and will be issued a new kit of drug product to be used from Week 4 through Week 8.
- Subjects will stop applying investigational product at Week 8 and will return investigational product at that visit.

- Subjects will come back for a 4-week post-treatment follow up visit at Week 12 (Day 84).
- Participant's safety will be monitored throughout the study. Safety will be assessed by monitoring reported adverse events, vital signs, clinical chemistry and hematology and overall tolerability of the investigational product.
- Subjects would be required to discontinue the investigational product under the following circumstances:
 - Development of an intercurrent illness that would jeopardize the safety, or significantly affect assessments of clinical status of a subject
 - Either at the discretion of the Investigator or at the participant's request
 - Development of any investigational product-related SAE
 - Suspected or laboratory-confirmed pregnancy

4.2 Number of Subjects and Sites

Approximately 130 subjects are planned to be enrolled, and assuming a 20% drop out rate, the planned overall sample size for this clinical trial is approximately 104 adult male and female subjects, 18 years of age and older with mild to moderate rosacea. Subjects will be randomized at a 1:1 ratio (B244: Vehicle) at about 8 clinical research centers in the United States.

